## 5 Treatment

### 5.1 Study treatment

#### 5.1.1 Investigational and control drugs

The Investigational treatments are as follows:

- Indacaterol acetate 75 µg capsules for inhalation, delivered via Concept1
- Indacaterol acetate 150 µg capsules for inhalation, delivered via Concept1

Indacaterol acetate will be provided as powder filled capsules with a Concept1 inhalation device.

**Under no circumstances is an alternative inhalation device to be used for the administration of indacaterol acetate capsules during the treatment period.**

Both doses of indacaterol acetate will be supplied by Novartis Drug Supply Management in blister packs, providing sufficient quantity of medication to last each patient between visits.

Patients will be instructed by study personnel on the correct technique and dosing instructions for the device. Dosing will be supervised by the site personnel. Dispensation instructions are provided in [Sections 5.5.2, 5.5.3, and 5.5.4](#). Instructions for use of the Concept1 device are provided in [Appendix 1](#).

#### 5.1.2 Additional treatment

At Visit 1 (Screening visit), patients will be provided with a salbutamol/albuterol inhaler to use as rescue medication on an “as needed” basis throughout the study ([Section 5.5.6](#)).

Additionally, patients will be supplied with a fluticasone propionate inhaler (Diskus®/Accuhaler®) and will be instructed to take 100 µg b.i.d for the trial duration (if not available in

a specific country, MDI dosed 125 µg should be used; in case these formulations are not available, then the closest equivalent to fluticasone propionate 100 µg b.i.d. should be given; MDI can be used with spacer). Patients taking another ICS (with or without controller medication) must be discontinued from that medication and begin the fluticasone propionate provided. Patients taking background LTRA may continue this throughout the study, if all other entry criteria are met.

## **5.2 Treatment arms**

Patients/subjects will be randomized at Visit 201 to one of the following two treatment arms in a ratio of 1:1

- Indacaterol acetate 75 µg o.d. delivered via Concept1 inhaler (in the morning)
- Indacaterol acetate 150 µg o.d. delivered via Concept1 inhaler (in the morning)

## **5.3 Treatment assignment and randomization**

At Visit 201, all eligible patients will be randomized via Interactive Response Technology (IRT) to one of the treatment arms above. The investigator or his/her delegate will contact the IRT after confirming that the patient fulfills all the inclusion/exclusion criteria. The IRT will assign a randomization number to the patient, which will be used to link the patient to a treatment arm and will specify a unique medication number for the first package of study drug to be dispensed to the patient. The randomization number will not be communicated to the caller.

The randomization numbers will be generated using the following procedure to ensure that treatment assignment is unbiased and concealed from patients/subjects and investigator staff. A patient randomization list will be produced by the IRT provider using a validated system that automates the random assignment of patient numbers to randomization numbers. These randomization numbers are linked to the different treatment arms, which in turn are linked to medication numbers. A separate medication list will be produced by or under the responsibility of Novartis Drug Supply Management using a validated system that automates the random assignment of medication numbers to packs containing the investigational drug(s). Randomization will be stratified by region.

The randomization scheme for patients will be reviewed and approved by a member of the COAR Randomization Group.

## **5.4 Treatment blinding**

Patients, investigator staff, persons performing the assessments, and data analysts will remain blind to the identity of the treatment from the time of randomization until database lock, using the following methods:

- Randomization data are kept strictly confidential until the time of unblinding, and will not be accessible by anyone involved in the study
- The identity of the treatment will be concealed by the use of study drugs that are all identical in packaging, labeling, and schedule of administration, appearance, taste, and odor.

The randomization codes associated with patients/subjects from whom PK samples are taken will be disclosed to PK bioanalysts who will keep PK results confidential until data base lock.

Unblinding will only occur in the case of patient emergencies (see [Section 5.5.9](#)) and at the conclusion of the study.

## **5.5 Treating the patient**

Sponsor qualified medical personnel will be readily available to advise on trial related medical questions or problems.

### **5.5.1 Patient numbering**

Each patient is uniquely identified by a Subject Number which is composed by the site number assigned by Novartis and a sequential number assigned by the investigator. Once assigned to a patient, the Subject Number will not be reused.

Upon signing the informed consent form, the patient is assigned the next sequential number by the investigator. The investigator or his/her staff will contact the IRT and provide the requested identifying information for the patient to register them into the IRT. The site must select the Case Report/Record Form (CRF) book with a matching Subject Number from the electronic data capture (EDC) system to enter data.

If the patient fails to be treated for any reason, the IRT must be notified within 2 days that the patient was not treated. The reason for not being treated will be entered on the CRF.

### **5.5.2 Dispensing the study drug**

Each study site will be supplied with study drug in packaging of identical appearance.

The study drug packaging has a 2-part label. A unique medication number is printed on each part of this label which corresponds to one of the investigational drugs. Investigator staff will identify the study drug package(s) to dispense to the patient by contacting the IRT and obtaining the medication number(s). Immediately before dispensing the package to the patient, investigator staff will detach the outer part of the label from the packaging and affix it to the source document (Drug Label Form) for that patient's unique subject number.

### **5.5.3 Handling of study and additional treatment**

#### **5.5.3.1 Handling of study treatment**

Study treatment must be received by a designated person at the study site, handled and stored safely and properly, and kept in a secured location to which only the investigator and designees have access. Upon receipt, all study treatment must be stored according to the instructions specified on the labels. Clinical supplies are to be dispensed only in accordance with the protocol. Technical complaints are to be reported to the respective Novartis Country Pharma Organization (CPO) Quality Assurance.

Medication labels will be in the local language and comply with the legal requirements of each country. They will include storage conditions for the study treatment but no information about the patient except for the medication number.

The investigator must maintain an accurate record of the shipment and dispensing of study treatment in a drug accountability log. Monitoring of drug accountability will be performed by monitors during site visits or remotely and at the completion of the trial. Patients/subjects will be asked to return all unused study treatment and packaging at the end of the study or at the time of discontinuation of study treatment.

At the conclusion of the study, and as appropriate during the course of the study, the investigator will return all unused study treatment, packaging, drug labels, and a copy of the completed drug accountability log to the Novartis monitor or to the Novartis address provided in the investigator folder at each site.

#### **5.5.3.2 Handling of additional treatment**

The following non-study drug will be monitored as follows:

The non-study drug must be received by a designated person at the study site, handled and stored safely and properly, and kept in a secured location to which only the investigator and designees have access. Clinical supplies are to be dispensed only in accordance with the protocol.

The investigator must maintain an accurate record of the shipment and dispensing of the non-study drug in a drug accountability log. Monitoring of drug accountability will be performed by monitors during site visits or remotely and at the completion of the trial. Patients will be asked to return all unused non-study drug and packaging at the end of the Run-in for the Run-in medication and at the end of the study or at the time of discontinuation of study drug for the rescue medication.

These medications are:

- Salbutamol (100 µg) or albuterol (90 µg) used as rescue medication from Visit 1 to Visit 299
- Fluticasone propionate (100 µg b.i.d. or acceptable dose equivalent as outlined in [Section 3.1](#) used as Background medication from Visit 1 to Visit 299

#### **5.5.4 Instructions for prescribing and taking study treatment**

Patients will be provided with medication as described in [Section 5.1](#).

Study medication prescribed and dispensed to the patient and all dose changes during the study must be recorded on the Dosage Administration Record CRF (e-CRF).

At Visit 1 all patients (and parent/legal guardian) will be instructed how to use the inhalers to administer rescue salbutamol/albuterol and the fluticasone propionate correctly. Patients and parent/legal guardian will be trained to use the peak flow meter and e-Diary as well.

Beginning at Visit 101, patients will be fully trained in the correct use of the Concept1 inhaler device used to administer study medication. Patients/parents who are unable to use the device correctly will not be eligible to enter the treatment epoch. Additional training devices will be supplied for demonstration purposes. At clinic visits the investigator should check the patient's use of the inhalational device to ensure that the child is using the device correctly. Additional device training may be provided if required.

At randomization, the patient will take a single inhalation, from the Concept1 device, while at the site.

**Patients, along with their parent/ legal guardian will be instructed to take one inhalation from the Concept1 device once daily, at approximately the same time each day during the two-week timeframe. Dosing should be done in the morning, following the patient's morning dose of fluticasone propionate.** Parents/legal guardian should be instructed to rinse the child's mouth after inhalation of study drug. Water used for mouth rinsing should be

spat out and should NOT be swallowed. Patients should take their 2nd dose of fluticasone propionate in the evenings.

**The time of study medication taken on morning of Day 13 (or one day prior to Day 14/Visit 299/End of Treatment) should be recorded by the parent and brought to the clinic at Visit 299. The child should not take study medication at home on the morning of Visit 299 (end of treatment visit). Study medication will be taken at the site on this day, under staff supervision.**

All kits of study treatment assigned by the IRT will be recorded/databased in the IRT. All used and unused study medication/packaging must be returned at each study visit and/or at the time of discontinuation.

The investigator must promote compliance by instructing the parent/legal guardian that their child needs to take the study treatment exactly as prescribed and by stating that compliance is necessary for the child's safety and the validity of the study. The parent/legal guardian must also be instructed to contact the investigator if their child is unable for any reason to take the study treatment as prescribed.

Instructions for use of the Concept1 device are provided in [Appendix 1](#).

### **5.5.5 Permitted dose adjustments and interruptions of study treatment**

Investigational treatment dose adjustments and/or interruptions are not permitted unless the investigator considers an interruption is necessary for the treatment of an adverse event.

These changes must be recorded on the Dosage Administration Record CRF.

In case of blind broken, the study medication is to be permanently discontinued.

### **5.5.6 Rescue medication**

At Visit 1 (Screening), all patients will be provided with a short acting  $\beta_2$ -agonist (100  $\mu$ g salbutamol/90  $\mu$ g albuterol via inhaler) which they will be instructed to use throughout the study as rescue medication. Nebulized salbutamol is not allowed as rescue medication throughout the entire trial. No other rescue treatment is permitted.

In order to standardize measurements, patients will be instructed to abstain from taking rescue medication (salbutamol) within 6 hours of the start of each visit where spirometry is being performed unless absolutely necessary. If rescue medication is taken within 6 hours prior to spirometry assessments, then the visit should be rescheduled to the next day if possible and the number of puffs of rescue medication taken recorded in the patient e-Diary.

Additionally, patients will be provided with fluticasone propionate 100  $\mu$ g (or dose equivalent see Section 5.1.2) via an inhaler, which should be taken b.i.d. beginning at Visit 1, or the next day if patient already took their daily ICS, and continue through the duration of the trial. If the patient is currently taking an ICS (with or without additional controller medication) the patient must switch to fluticasone provided at this visit. Fluticasone should be taken in the morning, prior to study drug, and in the evening. On days of study visits, patients should bring their fluticasone inhaler with them and take the dose at the site under supervision of study staff. Fluticasone use should also be captured in the eCRF.

The rescue salbutamol/albuterol and fluticasone will be provided to the patients by the study center and reimbursed locally by Novartis.

### 5.5.7 Concomitant medication

The investigator must instruct the patient to notify the study staff about any new medications he/she takes after the patient was enrolled into the study. All medications, procedures and significant non-drug therapies (including physical therapy and blood transfusions) administered after the patient was enrolled into the study must be recorded in the concomitant medications / significant non-drug therapies e-CRF.

Each concomitant drug must be individually assessed against all exclusion criteria/prohibited medication. If in doubt the investigator should contact the Novartis medical monitor before randomizing a patient or allowing a new medication to be started.

### 5.5.8 Prohibited medication

Prohibited asthma-related medications, as listed in [Table 5-1](#), must not be taken during the study. The specified minimum washout periods are described in [Table 5-1](#). The classes of medication listed in [Table 5-3](#) are not permitted to be taken during the study. The medications in [Table 5-2](#) are only permitted under the circumstances given. Each concomitant drug must be individually assessed against all exclusion criteria and the tables below to see if it is allowed. If in doubt, the investigator should contact the medical monitor before randomizing a patient or allowing a new medication to be started.

**Table 5-1 Prohibited asthma-related medications**

Class of medication	Minimum washout period starting at Visit 101 
Long-acting β2 agonists (LABA)	LABAs used b.i.d. must be discontinued 48 hours prior to Visit 101. LABAs used o.d. must be discontinued at least 14 days prior to Visit 101).
Long Acting Muscarinic Antagonist (LAMA)	Must be discontinued 7 days prior to Visit 101.
Short acting anticholinergics (SAMA)	Must be discontinued 8 hours prior to Visit 101.
Fixed combinations of short-acting β2-agonist and short-acting anticholinergics	Must be discontinued 8 hours prior to Visit 101.
Salbutamol/albuterol (SABA) provided at Visit 1 and throughout study as required for rescue medication	Must be withheld 6 hours prior to study visits beginning at Visit 101.
Short acting β2-agonists (SABAs) (other than Salbutamol/albuterol provided at Visit 1 for rescue medication)	Must be discontinued at Visit 1 and are not permitted during the study 
Intra-muscular depot corticosteroids	Must be discontinued 3 months prior to Run-in (Visit 101)
Systemic corticosteroids (Parenteral or oral)	Must be discontinued 3 months prior to Run-in (Visit 101)
Immunoglobulin E inhibitors (e.g. omalizumab)	Must be discontinued 6 months prior to Run-in (Visit 101)
Xanthines	Must be discontinued 7 days prior to Run-in (Visit 101)
Systemic mast cell stabilizers (e.g. cromoglycate, nedocromil, ketotifen)	Must be discontinued 7 days prior to Run-in (Visit 101)

 This table is not considered all-inclusive. Medications should be assessed for adherence to the indication and other inclusion/exclusion criteria.

 These medications are also prohibited if administered for other indications.

 SABA (salbutamol/albuterol rescue medication) should be withheld for at least 6 hours prior to spirometry measurements at clinic visits if possible. Clinic visits may be rescheduled if rescue medication were taken less than 6 hours prior to the spirometry assessments.

**Table 5-2 Medications allowed under certain conditions**

Class of medication	Condition under which medication is permitted
Topical Corticosteroids for treatment of eczema	Recommended doses and dosage regimens
Leukotriene antagonists and leukotriene synthesis inhibitors	Stable dose for at least 4 weeks prior to Visit 101.
Maintenance Immunotherapy for allergies	Stable dose for at least 3 months prior to Visit 101 and must continue unchanged for the duration of the study
Mucolytic agents not containing bronchodilators	If stabilized for at least 4 weeks prior to Visit 101 and throughout the trial.
Inactivated influenza vaccination, pneumococcal vaccination or any other inactivated vaccine	Not administered within 48 hours prior to a study visit
Intra-nasal corticosteroids	If an established pattern of use has been documented prior to Visit 101.

**Table 5-3 Other prohibited medications**

Class of medication	Minimum cessation period prior to Run-in (Visit 101)
Any drug with the potential to prolong QT interval	14 days or 5 half-lives, whichever is longer
Non-potassium sparing diuretics (unless administered as a fixed-dose combination with a potassium conserving drug)	7 days
Strong inhibitors of cytochrome P4503A	7 days
Other investigational drugs	30 days or 5 half-lives, whichever is longer
Noradrenaline reuptake inhibitors	7 days
Live attenuated vaccines	30 days

### **5.5.9 Emergency breaking of assigned treatment code**

Emergency treatment code breaks should only be undertaken when it is essential to treat the patient safely and efficaciously. Most often, study treatment discontinuation (TD) and knowledge of the possible treatment assignments are sufficient to treat a study patient who presents with an emergency condition. Emergency treatment code breaks are performed using the IRT. When the investigator contacts the system to break a treatment code for a patient, he/she must provide the requested patient identifying information and confirm the necessity to break the treatment code for the patient. The investigator will then receive details of the investigational drug treatment for the specified patient and a fax or email confirming this information. The system will automatically inform the Novartis monitor for the site and the Global Trial Leader (GTL) that the code has been broken.

It is the investigator's responsibility to ensure that there is a dependable procedure in place to allow access to the IRT/code break cards at any time in case of emergency. The investigator will provide:

- protocol number
- study drug name (if available)
- patient number

In addition, oral and written information to the subject must be provided on how to contact his/her backup in cases of emergency, or when he/she is unavailable, to ensure that un-blinding can be performed at any time.

## **5.6 Study completion and discontinuation**

### **5.6.1 Study completion and post-study treatment**

Completion of the study will be when the last patient has completed Visit 301 and as close as possible to serious adverse event (SAE) Follow-up at Day 44.

The investigator must provide Follow-up medical care for all patients who are prematurely withdrawn from the study, or must refer them for appropriate ongoing care.

### **5.6.2 Discontinuation of study treatment**

Discontinuation of study treatment for a patient occurs when study drug is stopped earlier than the protocol planned duration, and can be initiated by the patient, patient's parent/ legal guardian, or the investigator.

The investigator must discontinue study treatment for a given patient if, on balance, he/she believes that continuation would negatively impact the risk/benefit of trial participation.

Study treatment *must* be discontinued under the following circumstances:

- Patient's or parent/ legal guardian's wish
- Administration of a prohibited medication ([Table 5-1](#) and [Table 5-3](#))
- Worsening asthma as defined in [Section 6.5.6](#), as well as the following.
  - Excessive use of rescue medication (more than 200 µg salbutamol/ 180 µg albuterol four times per day for three consecutive days)
  - Abnormal test procedure results indicating risk for the patient on continued inhalation of the study drug including:
- Decline in PEF from the baseline PEF of  $\geq 20\%$  for one day or  $\geq 15\%$  for 3 consecutive days. The baseline PEF for the Run-in epoch would be the PEF taken at Visit 101. The baseline PEF (morning and evening) for the treatment epoch is calculated at visit 199 and is the mean of the best of the three daily PEF measurements over the past 14 days.
- Patients who experience moderate or severe asthma exacerbations ([Section 6.5.7](#))
- ECGs:
  - If the absolute QTcF  $\geq 450$  msec or an increase from baseline of  $> 60$  msec on 2 adequate ECGs at least a minute apart
  - 2nd or 3rd degree AV block
  - Atrial or ventricular arrhythmias (as judged clinically significant by the investigator)

- Any severe or serious adverse event considered possibly related to the study medication
- Patients who experience paradoxical bronchospasm: dyspnea and wheezing significantly increasing shortly after the administration of bronchodilator (*see Investigator's Brochure for more details*)
- Adverse events for which continued inhalation of the study drug would be detrimental
- If a patient develops a medical condition that requires use of prohibited treatment as per [Section 5.5.8](#), or if patient exhibits a behavior of non-compliance regarding prohibited medications.
- Pregnancy (see [Section 7.5](#))
- Any situation in which study participation might result in a safety risk to the patient
- Clinically significant abnormal laboratory value(s) (e.g., potassium below 3.0 mmol/L, LFT >3 x ULN)
- Any other protocol deviation that results in a significant risk to the patient's safety

If discontinuation of study treatment occurs, the patient should NOT be considered withdrawn from the study. The patient should return to the clinic as soon as possible, after discontinuation of study drug, for a study treatment discontinuation visit (Visit 299 will act as an early discontinuation visit in this case) and directly move into the Follow-up epoch.

Treatment discontinuation visit assessments detailed in the [Table 6-1](#) should be completed and recorded in the eCRF. The investigator must determine the primary reason for the patient's premature discontinuation of study treatment and record this in the End of treatment disposition page in the eCRF.

The investigator must also contact the IRT to register the patient's discontinuation from study treatment.

The data which must continue to be collected for all patients (including the patients discontinuing study treatment) are adverse event and serious adverse events for up to 30 days after drug discontinuation until the end of the study Follow-up visit (Visit 301).

Documentation of attempts to contact the patient should be recorded in the source documentation.

If study drug discontinuation occurs because treatment code has been broken, please refer to [Section 5.5.9](#).

If the patient fails to return for an end of study visit for unknown reasons, every effort should be made to contact them as specified in [Section 5.6.4](#).

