## **7.3 Liver safety monitoring**

To ensure patient safety and enhance reliability in determining the hepatotoxic potential of an investigational drug, a standardized process for identification, monitoring and evaluation of liver events has to be followed.

The following two categories of abnormalities / adverse events have to be considered during the course of the study (irrespective of whether classified/reported as (S)AE):

- Liver laboratory triggers, which will require repeated assessments of the abnormal laboratory parameter
- Liver events, which will require close observation, Follow-up monitoring and completion of the standard base liver CRF pages

Please refer to [Table 13-1 in Appendix 7](#) for complete definitions of liver laboratory triggers and liver events.

Every liver laboratory trigger or liver event as defined in [Table 13-1 of Appendix 7](#) should be followed up by the investigator or designated personal at the trial site as summarized below. Detailed information is outlined in [Table 13-2 in Appendix 7](#).

For the liver laboratory trigger:

- Repeating the liver function test (LFT) within the next week to confirm elevation.

These LFT repeats must be performed using the central laboratory if possible. If this is not possible, then the repeats can be performed at a local laboratory to monitor the safety of the patient. Repeats laboratory must then be performed at central laboratory as soon as possible. If a liver event is subsequently reported, any local LFTs previously conducted that are associated with this event must be reported on the Liver CRF pages.

- If the elevation is confirmed, close observation of the patient will be initiated, including consideration of treatment interruption if deemed appropriate.

For the liver events:

- Repeating the LFT to confirm elevation as appropriate
- Discontinuation of the investigational drug if appropriate
- Hospitalization of the patient if appropriate
- A causality assessment of the liver event via exclusion of alternative causes (e.g., disease, co-medications)
- An investigation of the liver event which needs to be followed until resolution.

These investigations can include serology tests, imaging and pathology assessments, hepatologist's consultancy, based on investigator's discretion. All Follow-up information, and the procedures performed must be recorded on appropriate CRF pages, including the liver event overview CRF pages.

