**Table 13-2 Follow Up Requirements for Liver Events and Laboratory Triggers**

Criteria	Actions required	Follow-up monitoring
Potential Hy's Law case a	
 
• Discontinue the study treatment immediately
 
• Hospitalize, if clinically appropriate
 
• Establish causality
 
• Complete liver CRF
 
	ALT, AST, TBL, Alb, PT/INR, ALP and γGT until resolution c (frequency at investigator discretion)
ALT or AST		
$> 8 \times \text{ULN}$	
 
• Discontinue the study treatment immediately
 
• Hospitalize if clinically appropriate
 
• Establish causality
 
• Complete liver CRF
 
	ALT, AST, TBL, Alb, PT/INR, ALP and γGT until resolution c (frequency at investigator discretion)
$> 3 \times \text{ULN}$ and INR $> 1.5$	
 
• Discontinue the study treatment immediately
 
• Hospitalize, if clinically appropriate
 
• Establish causality
 
• Complete liver CRF
 
	ALT, AST, TBL, Alb, PT/INR, ALP and γGT until resolution c (frequency at investigator discretion)
$> 5 \text{ to } \leq 8 \times \text{ULN}$	
 
• Repeat LFT within 48 hours
 
• If elevation persists, continue Follow-up monitoring
 
• If elevation persists for more than 2 weeks, discontinue the study drug
 
• Establish causality
 
• Complete liver CRF
 
	ALT, AST, TBL, Alb, PT/INR, ALP and γGT until resolution c (frequency at investigator discretion)

Criteria	Actions required	Follow-up monitoring
> 3 × ULN accompanied by symptoms b	
 
Discontinue the study treatment immediately
 
Hospitalize if clinically appropriate
 
Establish causality
 
Complete liver CRF
 
	ALT, AST, TBL, Alb, PT/INR, ALP and γGT until resolution c (frequency at investigator discretion)
> 3 to ≤ 5 × ULN (patient is asymptomatic)	
 
Repeat LFT within the next week
 
If elevation is confirmed, initiate close observation of the patient
 
	Investigator discretion Monitor LFT within 1 to 4 weeks
ALP (isolated)		

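### Section 5.6.2 names LFT >3 x ULN as a must-stop value, but Section 7.3 and Table 13-2 only repeat and observe isolated ALT/AST of >3 to 5 x ULN, and the 2-week stop for >5 to 8 x ULN cannot act within a 14-day course

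*Protocol*

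**What the plan says.** Protocol Section 5.6.2 opens its list with "Study treatment *must* be discontinued under the following circumstances". One item on that list is "Clinically significant abnormal laboratory value(s) (e.g., potassium below 3.0 mmol/L, LFT >3 x ULN". The item sets no condition about symptoms, persistence or repeat testing.

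Section 7.3 separates liver laboratory triggers from liver events. Table 13-1 makes ALT/AST above 3 and up to 5 x ULN a trigger, and ALT or AST above 5 x ULN an event. For a trigger, Section 7.3 asks for a repeat within a week and then says "If the elevation is confirmed, close observation of the patient will be initiated, including consideration of treatment interruption if deemed appropriate". For an event its wording is "Discontinuation of the investigational drug if appropriate".

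Table 13-2 sets out the actions by level:

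- Asymptomatic ALT/AST >3 to 5 x ULN: repeat within a week, then "If elevation is confirmed, initiate close observation of the patient". No stop is given.
- ALT/AST >5 to 8 x ULN: repeat within 48 hours and keep monitoring, then "If elevation persists for more than 2 weeks, discontinue the study drug".
- ALT/AST >8 x ULN, or >3 x ULN with symptoms, with INR >1.5, or as a potential Hy's Law case: stop at once.

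Section 3.1 sets a 2-week treatment epoch, with the last dose given at Visit 299 (Day 14).

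**The concern.** One ALT value can lead to two different actions. At 4 x ULN without symptoms, a site working from Section 5.6.2 stops the drug, while a site working from Table 13-2 repeats the test and goes on dosing. I found no text that says which section prevails.

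The >5 to 8 x ULN row has a second fault. Its stop needs the elevation to last longer than the whole planned treatment course. It looks like standard wording from a longer trial, and here it does nothing for an elevation first found on treatment.

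These are safety rules for children aged 6 to 11. What is at stake is consistent handling of a raised liver test across sites, not the estimation of FEV1.

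**Working it through.** The plan gives no derived figure on this point to reproduce. The check sets the rules side by side and then counts days.

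**1. The rules at given ALT/AST multiples** (asymptomatic, normal INR and bilirubin)

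| ALT/AST (x ULN) | Section 5.6.2 example | Table 13-2 |
|---|---|---|
| 2.9 | no stop | no action |
| 3.1, 4, 5 | stop | repeat and observe |
| 5.1, 8 | stop | stop only after more than 2 weeks |
| 8.1 | stop | stop at once |

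The sections agree up to 3 x ULN and above 8 x ULN. They differ throughout the range between.

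**2. When the 2-week clause can act**

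Inputs: first dose on Day 1 and last planned dose on Day 14 (Section 3.1, Table 6-1); persistence of more than 14 days (Table 13-2). I count from the day of the sample, which is the count most favourable to the clause.

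First whole day on which an elevation seen on Day d has lasted more than 14 days: d + 15.

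| First seen | Clause acts | Days after last dose |
|---|---|---|
| Day 1 | Day 16 | 16 − 14 = 2 |
| Day 2 | Day 17 | 3 |
| Day 7 | Day 22 | 8 |
| Day 14 | Day 29 | 15 |

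There are two exceptions:

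- Visit 299 may be rescheduled. A slip of at least 16 − 14 = 2 days would bring the Day 1 case inside treatment.
- An elevation already present at Visit 101, 14 days before Day 1, would pass 14 days on Day 2. Exclusion criterion 18 removes children with clinically significant Visit 101 values, so this needs a value that was not considered significant then.

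**3. Which samples can expose the conflict**

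Section 6.5.4 schedules safety laboratory tests at Visits 101, 199 and 299.

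- Visit 101 is an eligibility sample.
- The Visit 299 sample is drawn within 2 hours before the last dose (Table 6-3).
- The Visit 199 sample is drawn within 2 hours before the first dose and goes to a central laboratory. The child is randomised the same day once FEV1 qualifies (Table 6-2), and I found no requirement to have the liver result first.

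So 1 of 3 scheduled samples can return a result between randomisation and the last dose. Unscheduled tests add to that.

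**4. Would the replacement rules act in time?**

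Laboratory turnaround t is not stated; I assume 1 to 5 days. For a Day 1 sample:

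- Stop on the first result above 3 x ULN: Day 1 + t, that is Day 2 to Day 6.
- Stop when a 48-hour repeat confirms: first result on Day 1 + t, repeat by Day 3 + t, repeat result by Day 3 + 2t. For t = 1, 2, 3, 4, 5 this gives Day 5, 7, 9, 11, 13. At t = 6 it gives Day 15, which is too late.

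Both rules act before the Day 14 dose over the assumed range.

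**The case against.** The strongest reply is that Section 5.6.2 is conditional. It speaks of clinically significant values and gives LFT >3 x ULN only as an example. Appendix 6 sets no study-specific criteria and leaves significance to the investigator, so a site that considers 4 x ULN not significant breaches nothing. A site that stops at 3 x ULN satisfies every section, so the ambiguity errs on the strict side. This lowers the weight but does not remove the mismatch. A site following Table 13-2 can comply with Section 5.6.2 only by deciding that the protocol's own example of significance is not significant.

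A reader might infer that nothing compels a stop at >5 to 8 x ULN. The documents do not support that. The Section 5.6.2 example covers the band, and there are further routes:

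- the discretionary stop in Section 7.3;
- the item "Any severe or serious adverse event considered possibly related to the study medication";
- the Section 5.6.2 duties to stop when risk outweighs benefit or safety is at risk;
- SAE reporting of medically significant liver events under Section 6.5.4.4.

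What stands is that these further routes rest on case-by-case assessment, and the one fixed threshold is the one Table 13-2 contradicts.

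A reader might also see a contradiction in the asthma rules. Section 5.6.2 requires a stop for "Worsening asthma as defined in" Section 6.5.6, and the night-awakening criterion there lets a child continue at the investigator's discretion. The documents do not support calling this a contradiction. The exception is written inside the definition that Section 5.6.2 imports, so the ordinary reading carries it over. At most the wording could be clearer.

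**Conclusion.** The point holds for the liver rules. Section 5.6.2 conflicts with Section 7.3 and Table 13-2 for isolated, asymptomatic ALT/AST between 3 and 8 x ULN. The persistence clause for >5 to 8 x ULN is ineffective on the planned schedule for any elevation first seen on or after Day 1: it acts between Day 16 and Day 29, 2 to 15 days after the last dose.

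The late clause alone does not leave children unprotected, because Section 5.6.2 still applies. The fault is that sites are given two answers and no order of precedence.

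Practical reach is small: one of three scheduled samples, plus unscheduled tests. The day counts rest on the 14-day schedule being kept and on the two exceptions shown not arising. Nothing here changes the primary endpoint, the 80 to be randomised or the 72 evaluable. It should be fixed because it is a paediatric safety rule and the repair is cheap.

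**What to change.** Keep the Section 5.6.2 item as worded, including the term LFT, and add that it prevails over Section 7.3 and Table 13-2 during the 2-week treatment epoch. Amend Section 7.3 and the Table 13-2 rows for ALT/AST >3 to 5 and >5 to 8 x ULN to say the same.

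Do not narrow LFT to ALT or AST in Section 5.6.2. Table 13-2 also uses LFT for the repeat tests in its isolated ALP and bilirubin rows, so narrowing it would drop those from the named example. Because the isolated ALP row has no stop, the sponsor should confirm when amending that the precedence statement is meant to cover ALP above 3 x ULN.

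At a minimum, replace the more-than-2-weeks condition in the >5 to 8 x ULN row with a stop when the 48-hour repeat confirms the elevation. That makes the row effective within treatment but leaves the >3 to 5 x ULN mismatch in place.

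Optionally, repeat the night-awakening exception from Section 6.5.6 in Section 5.6.2, as a clarification only.

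Cost: amendment wording and a site notice. No patients, visits or scheduled samples are added. The downside is an occasional extra treatment discontinuation.
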